1.2 Protocol Summary

The objective of this post-market clinical follow-up study is to evaluate safety endpoints in patients receiving PhotoFix® Decellularized Bovine Pericardium (PhotoFix) as a patch within a vascular repair or reconstruction procedure. PhotoFix is prepared from bovine pericardium, which is stabilized using a dye-mediated photo-oxidation process and sterilized using aseptic processing techniques. The primary endpoint for patients with carotid artery stenosis (CAS) undergoing carotid endarterectomies (CEA) will be rate of ipsilateral central neurologic events; the primary endpoint for all other vascular procedures will be primary patency. The secondary endpoints include all-cause reoperation rate, device-related reoperation rate, explant rate, restenosis rate, secondary patency (hemodialysis access repair (HAR) only) and survival. A goal of 100 patients will be enrolled at approximately 10 sites. The enrollment period will span a minimum of 8 months from Institutional Review Board (IRB) approval and site activation. Candidates for this study are adults who require vascular repair or reconstruction surgery that necessitates the use of a patch. Patients will be consented pre-operatively and enrolled patients will be followed for approximately 6 months after PhotoFix surgery. Data will be collected at 5 time points: baseline (pre-operatively), intra-operatively, 1 month post-operatively, 3 months post-operatively, and 6 months post-operatively. Patients will be required to return to the office for the 3 visits occurring after hospital discharge. Follow-up data collection will focus on the

safety endpoints; data will be abstracted from the patient's medical record and collected from patient self-report. Study specific testing, including imaging and laboratory testing, will not be required.

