3.4.6 Follow-up Visits

The patients will be asked to return for 3 post-operative visits at 1, 3, and 6 months after surgery. Available data from post-operative imaging reports will be collected, as is applicable to the study and entered into the Imaging Evaluation eCRF (Appendix D); the imaging is not a requirement of the study. Clinical data for all follow-up visits will be entered into the Follow-Up Evaluation eCRF (Appendix D). This form will collect data on post-operative recovery. The following measures will be monitored and documented per indication, but may include:

- Visit date
- Study status
- Loss of patency/ Evidence of restenosis
- Reoperations / vascular surgeries required post-op
- Any adverse events, explants, or other mortality
- Post-operative imaging data

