6.1 Study Endpoints & Variables

In the case of CEAs, the primary endpoint of the study will be rate of ipsilateral central neurologic events.

- Ipsilateral central neurologic events: Transient ischemic attack, amaurosis fugax, stroke, and symptomatic carotid occlusion.

In the case of all other (non-CEA) vascular procedures, the primary endpoint of the study will be primary patency in the target artery or vein.

- Primary patency (of target vessel): Loss of patency will be determined by the loss of previously palpable pulses, patients presenting with recurrent symptoms, a drop in ABI >0.15 in the case of lower limb artery repair, Doppler ultrasound findings of occlusion, angiography of the affected vessel or a combination of these.

The secondary endpoints of the study will include: overall survival rate, all-cause reoperation rate, device-related reoperation rate, explant rate, restenosis rate, adverse event rate, and secondary patency (HAR only).

- Overall Survival:
 - Early mortality: Death < 30 days following PhotoFix implantation.
 - Late mortality: Death ≥ 30 days following PhotoFix implantation, until last day of follow-up.
- All-Cause Reoperation Rate: The total number of reoperations required in patients over the follow-up period, which include the repair or alteration of the surgical area around the patch.

- **Device-Related Reoperation Rate:** The total number of unplanned reoperations required in patients over the follow-up period, which are determined by the surgeon to be device-related.
- **Explant Rate:** The total number of device explants over the course of follow-up. Explants will include the removal of PhotoFix for any reason after implantation.
- **Restenosis Rate:** The total number of documented cases of stenosis documented as the recurrence of abnormal narrowing of a vessel after corrective surgery.
- **Adverse Event Rate:** The total number of any unfavorable and unintended sign (including an abnormal laboratory finding), symptom, or disease temporarily associated with the use of a device, whether or not related to the device.
- **Secondary Patency (HAR only):** The time from implantation to the point where the access is abandoned.

Statistical analysis will be used to assess all study endpoints as applicable.

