9. Perioperative or Post-Operative Adverse Events *If yes, fill out the Adverse Event eCRF.	 Yes  No
If yes, timing of event	 Peri-Operative  Post-Operative
10. Length of Implanted Patch (cm)	 Unknown
11. Width of Implanted Patch (cm)	 Unknown

Follow-Up eCRF	
Study Subject ID	
1. Date of Visit	/ / Month/Day/Year
2. Indicate Visit Number *If Visit 5, fill out End of Study eCRF.	 Visit 3, 1 month post-op  Visit 4, 3 months post-op  Visit 5, 6 months post-op  Unscheduled Visit
3. Indicate Current Subject Status *If withdrawn, fill out End of Study eCRF.	 Active  Withdrawn
4. Were there any post-operative Adverse Events since last study visit? *If yes, fill out the Adverse Event eCRF.	 Yes  No
5. Was patency lost in the target artery/vein since the last study visit? *If yes, fill out the Adverse Event eCRF.	 Yes  No
If yes, indicate the number of instances that patency was lost	
If yes, indicate date(s) patency was lost	/ / (most recent) Month/Day/Year / /  N/A Month/Day/Year / /  N/A Month/Day/Year
If yes, indicate reason(s) patency was lost	 Aneurysm  Infection  Restenosis  Thrombosis  Other: _____ *Select all that apply
If yes, was a surgical (open or endovascular) procedure performed to re-establish patency?	 Yes  No  Unknown
If yes, was any loss of patency PhotoFix-related?	 Definitely  Probably  Possibly  Unrelated
If yes, was patency successfully re-established for the most recent event?	 Yes  No  Unknown
6. Did the patient undergo any vascular	 Yes

Follow-Up eCRF	

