surgery (open or endovascular) since the last study visit? *If yes, fill out the Adverse Event eCRF.	 No  Unknown
If yes, date surgery occurred	/ / Month/Day/Year
If yes, indication for surgery?	 Infection  Re-establish Hemodialysis Access Patency  Rupture  Stenosis  Thrombosis  Other: _____ *Select all that apply
If yes, describe the surgical procedure	
If yes, did the surgery involve PhotoFix or the surrounding patch area?	 Yes  No
If yes, was PhotoFix explanted? *If Partially or Completely, fill out Explant eCRF	 No  Partially  Completely
If yes, was the need for surgery related to PhotoFix?	 Definitely  Probably  Possibly  Unrelated
7. Has there been evidence of restenosis since the last study visit?	 Yes  No  Unknown
If yes, was an imaging evaluation performed *If yes, complete the Imaging Evaluation eCRF	 Yes  No  Unknown
If yes, indicate the degree of restenosis.	 Unknown
8. Describe any other significant events which have occurred since the last follow-up visit.	 None

Adverse Event eCRF	
Study Subject ID	
1. Date Adverse Event Reported	____ / ____ / ____ Month/Day/Year
2. Is this an update to a previously reported event?	 Yes  No
3. Start Date	____ / ____ / ____ Month/Day/Year
4. Stop Date	____ / ____ / ____ Month/Day/Year

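### The Follow-Up eCRF has no prompt for TIA, amaurosis fugax or stroke, so brief events in the CEA primary endpoint may be missed at scheduled visits

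*Protocol*

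**What the plan says.** Protocol 6.1 sets two primary endpoints. For the carotid group, "In the case of CEAs, the primary endpoint of the study will be rate of ipsilateral central neurologic events", made up of "Transient ischemic attack, amaurosis fugax, stroke, and symptomatic carotid occlusion". For all other procedures it is primary patency of the target vessel.

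The Follow-Up eCRF (Protocol Appendix D) is completed at the 1-, 3- and 6-month visits. Item 4 asks "Were there any post-operative Adverse Events since last study visit", Yes or No, and a Yes opens the Adverse Event eCRF. Item 5 asks "Was patency lost in the target artery/vein since the last study visit", with follow-on fields for number, dates, cause and relation to the patch. Item 6 asks about vascular "surgery (open or endovascular) since the last study visit", and item 7 about restenosis. Item 8 is a free-text box for other notable events.

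Protocol 3.4.6 lists what follow-up may record. The list names "Loss of patency/ Evidence of restenosis", reoperations and adverse events in general, but no neurologic measure. Protocol 1.2 says of follow-up that "data will be abstracted from the patient's medical record and collected from patient self-report", and that no study-specific testing is required.

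SAP 2.9.1 provides a query when the Follow-up and Adverse Event forms disagree about patency. It has no such rule for neurologic events. SAP 2.9.1 and 2.10 report the CEA endpoint as counts and percentages, for each component and for any of them.

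**The concern.** The two primary endpoints are collected in different ways. Loss of patency is asked about by name at every visit, with structured detail. TIA, amaurosis fugax and stroke are not. They reach the database at a scheduled visit only if the patient or the site connects them with a general question.

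This matters most for TIA and amaurosis fugax. They resolve, so they may leave nothing to find at an office visit one to three months later. They may not have led to a chart entry, and a patient may not regard them as a complication. A stroke is more likely to be in the record.

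The study has a single arm (Protocol 3.4.1), so no comparator shares the same loss. Any missed event lowers the reported CEA rate, and a low rate could not be told apart from incomplete questioning. The degree of loss could also vary across the roughly 10 sites, since nothing standardises the questioning.

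**Working it through.** No figure in the plan bears on this point: the documents give no CEA subgroup size, expected event rate or capture probability. The check is therefore mainly a reading of the forms.

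**Step 1. Each endpoint component against the Follow-Up eCRF**

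| Component | Named in items 1–8? | Nearest item |
|---|---|---|
| TIA | No | 4 (general), 8 (free text) |
| Amaurosis fugax | No | 4, 8 |
| Stroke | No | 4, 8 |
| Symptomatic carotid occlusion | Not by name | 5 (patency of target vessel), 4, 8 |

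Item 5 is not restricted to non-CEA patients, so an occluded carotid patch site should produce a Yes and an Adverse Event eCRF. That component is partly covered.

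Items 6 and 7 offer Unknown. Item 4 does not, so a visit at which neurologic symptoms were never discussed is stored as No.

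**Step 2. Routes outside the Follow-Up eCRF**

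- The Operative Assessment eCRF, item 9, covers events around the operation.
- Patients are told to contact the investigator about complications (Protocol 3.4.5), and unscheduled events are collected (3.2).
- Charts are abstracted (1.2), and full source verification is intended (7). These recover only what someone wrote down.
- The Adverse Event eCRF, item 5, has a tick box for each of the four components, but it is opened after an event is recognised. It classifies events and does not elicit them.

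None of these is a neurologic question put to every CEA patient at every visit. No neurologic examination or symptom questionnaire is specified.

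**Step 3. Side**

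The endpoint is ipsilateral. The operated side is on the Medical History eCRF (item 6), but the Adverse Event eCRF has no side field, only a free-text description.

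**Step 4. Illustration (all inputs assumed)**

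Let p be the true event rate, f the share of patients with events who had only TIA or amaurosis fugax, and s the fraction of those picked up. Strokes and occlusions are assumed fully captured.

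Expected observed rate = p × [1 − f × (1 − s)]

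Take 50 CEA patients, 5 with a true event (p = 0.10), 3 of them transient only (f = 0.60):

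- s = 0.8: (2 + 0.8 × 3)/50 = 4.4/50 = 8.8%
- s = 0.5: (2 + 0.5 × 3)/50 = 3.5/50 = 7.0%
- s = 0: 2/50 = 4.0% (an extreme, given the routes in step 2)

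The expected loss is 0.6 patients at s = 0.8 and 1.5 at s = 0.5. Each patient is 1/50 = 2 percentage points.

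A second view is the chance of reporting no event at all, (1 − p × c)^N, where c is capture over all components. With N = 50 and p = 0.05:

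| Capture c | Expected events seen | Chance of none |
|---|---|---|
| 100% | 2.50 | 0.08 |
| 90% | 2.25 | 0.10 |
| 70% | 1.75 | 0.17 |
| 50% | 1.25 | 0.28 |

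Over N = 30 to 70 and p = 3% to 10%, the chance of none runs from 0.001 to 0.40 at full capture and from 0.03 to 0.64 at 50% capture. Overall capture as low as 50% would require missing more than brief events if strokes are well documented.

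**The case against.** The other side has a fair case, and part of it stands.

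- A reader might infer that transient events are under-reported. The documents hold no data on capture, so they support only a risk.
- A reader might infer that item 4 is the sole route in. It is not: step 2 lists others, and item 8 is a second open prompt. Item 4 is itself a question put at three visits, so capture is solicited, though not symptom-specific.
- A reader might infer that CEA patients are questioned only about someone else's endpoint. Item 5 bears on carotid occlusion, and reoperation and restenosis are secondary endpoints for all enrolled patients (SAP 2.13, 2.16).
- Protocol 4.1 names all four components as a main focus of the complication analysis, and 3.4.6 does list adverse events. Sites are told that these events matter.
- The 24-hour reporting rule in Protocol 4.3 starts on knowledge of the event. It fails for any unknown event and adds nothing specific here.
- The study is descriptive. The sample size has no formal statistical basis (SAP 2.20), so no test or decision threshold is at stake.
- Direct questions about temporary weakness or numbness can elicit contralateral or non-vascular symptoms and push the rate up unless someone classifies them.

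What remains is that none of the existing routes asks a CEA patient about transient neurologic symptoms. The last bullet is a reason to design the new item with care, not to leave it out.

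**Conclusion.** The point holds as a weakness in data collection. At scheduled visits, TIA, amaurosis fugax and stroke rest on general questions, while the non-CEA primary endpoint has its own structured item. Brief TIA or amaurosis fugax may be missed, and any such loss biases the CEA rate low.

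The size cannot be derived from the documents. The 7.0% to 8.8% against a true 10% depends entirely on an assumed 50 CEA patients, 5 events, a 3-in-5 transient share and 50% to 80% pick-up. It shows only that one or two missed patients are visible in a group this small. The conclusion itself rests on the form content alone. The change is worth making because it is cheap and protects a primary endpoint that has no comparator.

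**What to change.** 1. Add a (CEA only) item to the Follow-Up eCRF at visits 3, 4 and 5. For each of TIA symptoms, temporary loss of vision in one eye, stroke and symptomatic carotid occlusion since the last visit, record Yes, No or Unknown, with the date and the side relative to the operated carotid.
2. If any answer is Yes, require the Adverse Event eCRF, where the investigator classifies the event. Count only ipsilateral events so classified in the primary endpoint.
3. Add ipsilateral central neurologic events (CEA) to the list in Protocol 3.4.6.
4. Add to SAP 2.9.1 a query rule between the two forms for these events, modelled on the patency rule.

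The forms already use CEA-only items and all three visits are planned, so no new visit or test is needed. The cost is about a minute per CEA visit, some non-specific symptoms for the investigator to classify, and possibly a higher observed rate.

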#### **Primary Patency:**

- Time from PhotoFix implantation to the time when patency in the vessel is documented as lost
  - Loss of patency includes loss of previously palpable pulses, presentation of recurrent symptoms, a drop in ABI $>0.15$  in the case of lower limb artery repair, Doppler ultrasound findings of occlusion, angiography of the affected vessel or a combination of these.

Loss of patency will also be considered if an intervention to restore or maintain patency is documented. In the event that loss of patency is documented as “no” on the Follow-up eCRFs and evidence of an intervention involving patency restoration is reported on the Adverse Event eCRF, a query will be issued and resolved appropriately.

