## **2.11. Primary Patency**

A Kaplan-Meier (KM) survival curve for primary patency will be estimated for enrolled patients who received PhotoFix for any non-CEA procedure. Additional KM plots for primary patency may be estimated by surgical indication but will be determined by the sample size of each subgroup; sample sizes of 20 patients or more will be considered to estimate meaningful plots.

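### The main patency question on the follow-up form has no 'not assessed' answer, so primary patency in non-CEA procedures is likely to be overstated by an amount the form cannot show

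*Protocol*

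**What the plan says.** SAP section 2.9.1 defines the non-CEA primary endpoint as "Time from PhotoFix implantation to the time when patency in the vessel is documented as lost". Section 2.11 gives the analysis: "A Kaplan-Meier (KM) survival curve for primary patency will be estimated for enrolled patients who received PhotoFix for any non-CEA procedure". Any further curves are by surgical indication. Neither section states a censoring rule, a count of vessels assessed or a sensitivity analysis. Section 2.21 says only that entries of unknown will show in the listings.

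The main data source is item 5 of the Follow-Up eCRF (Protocol Appendix D): "Was patency lost in the target artery/vein since the last study visit". Its boxes are Yes and No. Item 6 (vascular surgery) and item 7, "Has there been evidence of restenosis since the last study visit", each add Unknown, as do two of item 5's own sub-questions. The Operative Assessment form even lets the surgeon record that patch sidedness was not checked.

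Protocol section 1.2 states: "Study specific testing, including imaging and laboratory testing, will not be required". Section 3.4.6 says of follow-up imaging that "the imaging is not a requirement of the study".

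Two provisions widen the evidence. Protocol section 6.1 accepts clinical signs: "Loss of patency will be determined by the loss of previously palpable pulses, patients presenting with recurrent symptoms", along with a fall in ABI, Doppler or angiography. SAP section 2.9.1 adds a second source: "Loss of patency will also be considered if an intervention to restore or maintain patency is documented". It also provides for a query when a No on the follow-up form conflicts with an intervention on the Adverse Event form.

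**The concern.** At some visits nobody will have established whether the vessel is patent. This is most likely for targets such as the renal, superior mesenteric or internal iliac vessels and deep veins, all listed on the Medical History eCRF, where pulses or ABI may not settle the matter. The site must still choose Yes or No, and without evidence of loss No is the natural choice. The form has no field for how patency was judged, so 'assessed and patent' and 'not assessed' look the same in item 5.

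The study has no comparator and no performance goal, so the patency estimate is itself the main non-CEA result. If unassessed vessels are counted as patent, that estimate leans in the device's favour and a reader of the report cannot tell by how much.

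**Working it through.** The documents state no expected patency rate, share of silent losses or share of visits without assessment, so there is no plan figure to reproduce. Every rate below is an assumption, and each calculation supposes that an unassessed vessel is entered as No.

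**1. Simple proportions.** Let N be the non-CEA patients, L the documented losses and U the vessels not assessed but entered as No. Reported patency is 1 − L/N. Among assessed vessels only, it is 1 − L/(N − U). If every unassessed vessel were lost, it is 1 − (L + U)/N. With L/N = 10%:

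| U/N | As planned | Assessed only | Worst case |
|---|---|---|---|
| 10% | 90.0% | 88.9% | 80% |
| 20% | 90.0% | 87.5% | 70% |
| 30% | 90.0% | 85.7% | 60% |
| 40% | 90.0% | 83.3% | 50% |

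For example, at 20%: 1 − 0.10/0.80 = 87.5% and 1 − 0.30 = 70%. The planned figure does not move with U. Its distance from the worst case is U/N, which item 5 cannot supply.

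**2. Visit model.** Assume exponential time to loss, visits at days 30, 91 and 183, true six-month loss p, a share s of losses silent, and a share u of visits unassessed. Symptomatic losses are always recorded; silent ones are recorded only at a later assessed visit. With F(t) = 1 − (1 − p)^(t/183), a silent loss before day 30 escapes if all three visits are unassessed, one between days 30 and 91 if the last two are, and one after day 91 if the last is. Recorded loss is therefore

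R = p − s × [F(30)u³ + (F(91) − F(30))u² + (F(183) − F(91))u].

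For p = 20%: F(30) = 0.0359, F(91) = 0.1050, F(183) = 0.2000.
- u = 50%: the bracket is 0.0045 + 0.0173 + 0.0475 = 0.0693. With s = 60%, R = 20 − 4.2 = 15.8%. With s = 30%, R = 20 − 2.1 = 17.9%.
- u = 20%: the bracket is 0.0003 + 0.0028 + 0.0190 = 0.0221. With s = 60%, R = 20 − 1.3 = 18.7%.

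For p = 40%, s = 60%, u = 50%: F(30) = 0.0803 and F(91) = 0.2243, so the bracket is 0.0100 + 0.0360 + 0.0878 = 0.1339 and R = 40 − 8.0 = 32.0%.

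For p = 10%, s = 30%, u = 20%: F(30) = 0.0171 and F(91) = 0.0510, so the bracket is 0.0001 + 0.0014 + 0.0098 = 0.0113 and R = 10 − 0.3 = 9.7%.

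The last two cases are the largest and smallest shortfalls over p of 10, 20 and 40%, s of 30 and 60%, and u of 20 and 50%.

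**3. Censoring at the last assessed visit instead.** These values come from simulation (400,000 patients per scenario) and agree between runs to about 0.2 point.

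| True loss | Silent | Unassessed | Planned curve | Censored curve |
|---|---|---|---|---|
| 20% | 60% | 50% | 15.8% | 24.7% |
| 20% | 60% | 20% | 18.7% | 21.0% |
| 20% | 30% | 50% | 17.9% | 27.2% |
| 40% | 60% | 50% | 32.0% | 47.2% |

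Over the twelve scenarios the censored curve overstates loss by about 0.5 to 10.4 points. The cause is informative censoring: symptomatic losses are still counted after the last assessment, while event-free patients leave the risk set at that assessment. In the third row this curve is further from the truth than the planned one (7.2 points against 2.1).

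**4. Do the two curves bracket the truth?** Only if every symptomatic loss is recorded. With p = 20%, s = 60%, u = 20% and one in five symptomatic losses unrecorded, the planned curve falls by a further 0.2 × 0.4 × 20 = 1.6 points to about 17%. The censored curve gives about 19%. Both lie below 20%.

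**The case against.** The strongest reply is that nothing tells a site to enter No for a vessel it did not assess. Protocol section 6.3 requires source support for all data, section 6.5 provides queries for unanswered or unsupported items, and sections 6.6 and 7 intend full source verification. This stands against any claim that the form simply records unassessed vessels as patent. It does not close the gap, because a query on item 5 can end only in Yes, No or a blank.

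Second, three office visits are expected, and recurrent symptoms or lost pulses are enough to establish loss. This stands too. It confines the problem mainly to vessels that cannot be judged clinically, and the documents do not show how many there will be. Since the form does not record how patency was judged, nobody could show from it that a given vessel was checked.

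Third, item 5 is not the only source. Documented interventions count as loss and conflicts are queried. This catches treated losses; silent untreated ones remain.

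Fourth, a reader might infer that the reported figure is exactly the favourable bound and that all error runs one way. The documents do not support that. Recurrent symptoms, or an intervention only to maintain patency, can count an open vessel as lost. A missed visit or withdrawal may leave no item 5 answer at all, and the SAP does not say when such a patient is censored.

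Fifth, a reader might infer that the lost distinction can never be recovered. The Imaging Evaluation eCRF records date, visit, modality and stenosis, with Unknown available, and source notes exist. Part of it could be rebuilt; assessments by pulse or ABI could not be rebuilt from the forms.

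Finally, sampling error may be larger than the bias. At an assumed 50 non-CEA patients and 20% loss, the 95% half-width is 1.96 × √(0.2 × 0.8/50) = 11.1 points, against 1.3 to 4.2 points of shortfall in the 20% rows above. That is fair on scale, but the bias comes on top of sampling error and is not visible in the output.

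**Conclusion.** The point holds as a likely overstatement of primary patency. The form for the main endpoint source cannot record that patency was not assessed, no test is mandated, and the SAP has no rule or sensitivity analysis for unassessed vessels. Followed as written, the plan tends to count them as patent.

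In the scenarios run, recorded six-month loss is about 0.3 to 8 points too low. It is near the bottom of that range when few visits are unassessed or most losses cause symptoms. These sizes rest wholly on assumed loss, silent-loss and non-assessment rates, and on sites entering No when patency was not assessed. The documents fix the likely direction but not the amount.

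It would be tempting to present the planned and censored curves as limits that must contain the truth. They should not be, since the result fails once some symptomatic losses go unrecorded. This deserves correction but does not undermine the study, which is descriptive and has no powered hypothesis.

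**What to change.** 1. Add 'Not assessed' as a third response to Follow-Up eCRF item 5.
2. In SAP section 2.11, report the number of vessels actually assessed for patency at each visit.
3. Keep the planned Kaplan-Meier curve, and label it as counting unassessed vessels as patent.
4. Add two sensitivity analyses: (a) a curve censored at the last visit with patency assessed, with a warning that this censoring is informative and can overstate loss; (b) a worst-case figure that counts as lost any vessel never assessed or not assessed at its last visit.
5. Do not describe the planned and censored curves as bounds on the truth.

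The cost is one response option, a table of counts and a little more analysis. No new testing or change in patient care is needed. The downside for the sponsor is that patency is reported as a range, less favourable than the single figure. The form change works best before follow-up data are entered; afterwards the distinction has to be rebuilt from charts and imaging forms, and only in part.
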